To assess for adverse drug events, the research coordinator will review patient symptomology, vital signs and laboratory values. The research coordinator will be trained by the study pharmacists in identifying medication errors and adverse drug events, determining causality and grading the severity. To ensure objectivity and consistency in recording these events across both study cohorts, a number of safeguards will be instituted. First, the study investigators will utilize the same research coordinator to record all medication errors and adverse drug events. Second, this research coordinator will be completely independent of the telehealth intervention that is being performed and will be blinded to the patient’s randomized group. Third, only the medication errors and adverse drug events recorded by this research coordinator will be

used for data analysis. Finally, these patient assessments will be followed by an independent assessment by a clinical transplant pharmacist that is not associated with delivering the study intervention. This will ensure that event rates are not biased towards a higher capture rate in the intervention cohort, which will be receiving more intense scrutiny of their medication regimens by a clinical pharmacist.

E4 Study Outcome Measurements and Ascertainment

The primary outcome measure of this study will be the incidence and severity of medication errors and adverse drug events, which will be identified, categorized and compared between the intervention and control cohorts as detailed above and in the following sections. The exploratory outcome measures of this study are to compare the incidence and severity of acute rejections, infections, graft function, graft loss and death between research cohorts and measure the association between medication safety issues and these events. Demonstrating improvements in acute rejections, infections, graft loss or death within the intervention group will provide the data needed to design a larger, multicenter study (through dissemination efforts detailed at the end of this proposal). Additional data that will be gathered includes patient surveys to capture measures of sociodemographics, health literacy, depression, social support and trust. These are important variables that may modify or confound the impact of the intervention.

Study endpoint definitions and assessment plan:

The following will be used to define and capture data and events within this study:

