This analysis will incorporate the intent-to-treat principle, namely, all randomized participants will be included in the analysis according to their intervention assigned at baseline. The two groups will be compared using standard statistical analyses. Data will be reported using percentages for nominal and ordinal variables and compared using Fisher's exact test or Pearson's chi-squared test as appropriate. This includes baseline demographic and transplant characteristic variables, as well as the outcome variables of the incidence and severity of medication errors and adverse drug events, acute rejection and infections. For continuous variables with normal distribution, results will be reported using means and standard deviations with statistical comparison using Student's t-test for two independent samples. For *non-normally distributed* variables, the results will be reported using medians and interquartile ranges, with statistical comparison conducted using the Mann Whitney U test. Normal distribution of continuous variables will be assessed using normality plots and the Shapiro-Wilk test. Normal variance will be assessed using Levene's test for equality of variances. Results for graft and patient survival will also be reported using Kaplan-Meier survival curves and compared using the Log Rank test.

If it is determined that there are significant imbalances in baseline demographics or characteristics known to influence any of the outcome measures, multivariable modelling will be used to adjust for these differences. For nominal outcomes, binary logistic regression will be used in a standard entry fashion, which will include both the grouping variable and all known risk-factors. For continuous outcomes that demonstrate linearity

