in the relationship between dependent and independent variables, with a lack of serial correlation between covariates, homoscedasticity of the errors and normality of the error distribution, linear regression will be utilized in a similar manner. We will adjust for baseline values if the interventions are discrepant at baseline. This model will include the intervention arm and baseline response as fixed-effects and is known to lead to very precise inference.(7) If any of the four aforementioned assumptions are violated, then the data variables will either be transformed or appropriate substitute multivariable modelling will be used. Cox proportional hazard regression analysis will be used for time-dependent survival analyses involving the outcomes of graft and patient survival. For count outcomes, such as health care encounters, we will use Poisson regression; if the assumption of equal mean and variance is violated (over dispersion), we will use Negative Binomial regression. In all models, we will adjust for correlation of outcomes by including random effect terms. For all models that belong to the generalized linear model (linear, logistic, Poisson), we will use generalized estimating equations (GEE), and for survival outcomes, we will use frailty Cox regression.(8) We will use multiple imputation techniques to deal with missing data that is at random (MAR).(9) MAR assumes that the probability that an outcome is missing depends on observed outcomes. While mechanisms for missingness are likely to be MAR, we will also do sensitivity analysis for data missing not at random (MNAR) using methods from Little and Rubin.(9)

F4 Statistical Methods

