The two groups will be compared using standard statistical analyses. Data will be reported using percentages for nominal and ordinal variables and compared using Fisher's exact test or Pearson's chi-squared test as appropriate. This includes baseline demographic and transplant characteristic variables, as well as the outcome variables of the incidence and severity of medication errors and adverse drug events, acute rejection and infections. For continuous variables with normal distribution, results will be reported using means and standard deviations with statistical comparison using Student's t-test for two independent samples. For *non-normally distributed* variables, the results will be reported using medians and interquartile ranges, with statistical comparison conducted using the Mann Whitney U test. Normal distribution of continuous variables will be assessed using normality plots and the Shapiro-Wilk test. Normal variance will be assessed using Levene's test for equality of variances. Results for graft and patient survival will also be reported using Kaplan-Meier survival curves and compared using the Log Rank test.

F5 Missing Outcome Data

We will use multiple imputation techniques to deal with missing data that is at random (MAR).(9) MAR assumes that the probability that an outcome is missing depends on observed outcomes. While mechanisms for missingness are likely to be MAR, we will also do sensitivity analysis for data missing not at random (MNAR) using methods from Little and Rubin.(9)

F6 Unblinding Procedures

No unblinding procedures are necessary, as this is as open-label study.

G Data Handling and Record Keeping

G1 Confidentiality and Security

In order to protect subjects against any risk regarding loss of personal information, all obligations under the Health Portability and Accountability Act (HIPPA) will be met. Additionally, all data will be collected and stored through the secure network server and behind the MUSC firewall. We will use electronic CRF forms to gather all study information (redcap.musc.edu). Data will only be stored on campus computers under the MUSC secure network. Data collection forms will be maintained within an office, which is a locked office facility on campus. Only approved study members will have access to patient data.

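### Covariate adjustment depends on an undefined baseline imbalance and the plan does not say which result is then primary; fix at most two prognostic covariates in advance and always adjust

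*Combined protocol and SAP*

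**What the plan says.** F3 Analysis Plan puts baseline characteristics and the primary outcomes through the same unadjusted Fisher or Pearson tests. Multivariable modelling comes second and is conditional: "If it is determined that there are significant imbalances in baseline demographics or characteristics known to influence any of the outcome measures". Once it is invoked, nominal outcomes get a binary logistic model "which will include both the grouping variable and all known risk-factors". No list of risk factors and no limit on their number is given.

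For continuous outcomes, F3 has a second condition: "We will adjust for baseline values if the interventions are discrepant at baseline". Of the model that results, F3 says: "This model will include the intervention arm and baseline response as fixed-effects and is known to lead to very precise inference". For encounters it says: "For count outcomes, such as health care encounters, we will use Poisson regression", with negative binomial regression if the counts are overdispersed.

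F4 Statistical Methods repeats the unadjusted tests for baseline variables "as well as the outcome variables of the incidence and severity of medication errors and adverse drug events". It attaches no condition and does not mention the models.

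E4 Study Outcome Measurements and Ascertainment plans "patient surveys to capture measures of sociodemographics, health literacy, depression, social support and trust" and remarks: "These are important variables that may modify or confound the impact of the intervention". None of these is assigned to a model. Randomisation (D2, 2.e) is in blocks of 8 with no stated strata, so the design does not supply covariates either.

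**The concern.** There are two faults.

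First, the choice of analysis depends on the observed baseline data through a trigger that nobody can apply in only one way. If the trigger fires, the plan yields an unadjusted and an adjusted result for medication errors and for ADEs, and does not say which one counts.

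Second, the trigger is the wrong criterion. Under randomisation a baseline difference is chance, and testing it says nothing about whether a variable predicts the outcome. A strong predictor is worth adjusting for even when balanced, and a weak one is not worth it even when imbalanced. Prognostic value can be judged before the trial.

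At stake are the clarity of the primary result in an open-label trial and some precision from baseline data that are being collected anyway.

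**Working it through.** **Inputs from the documents.** F1: errors 64% in control, halved to 32%; grade 3+ ADEs 87%, reduced by 33% to 0.87 × 0.67 = 58.3%; two-sided alpha 0.05; 52 per arm evaluable; 85% retention. D1: 68 per arm. Expected completers: 68 × 0.85 = 57.8, taken as 58 per arm.

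**Assumptions.** The documents do not give the number, independence or strength of the covariates, nor a threshold for imbalance. I take p<0.05 as the trigger, independent variables, and two covariates of weak or strong joint prognostic value (log-odds SD 0.5 or 1.0, AUC about 0.63 or 0.74).

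**1. The plan's own power.** For errors at 52 per arm, power = Φ[(d√n − 1.96√(2p̄q̄)) / √(p₁q₁ + p₂q₂)], with d = 0.32 and p̄ = 0.48. This is Φ[(2.308 − 1.385)/0.669] = Φ(1.38) = 91.6%, against the stated 92%. For ADEs the same formula gives 91.9%, against the stated 94%. Both are within about two points, so the stated figures are accepted.

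**2. How often chance alone fires the trigger.** 1 − 0.95^k is 9.75% for k = 2, 18.5% for k = 4 and 40% for k = 10.

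**3. Power at 58 per arm.** These are simulations of 20,000 trials per setting (Monte Carlo error up to 0.3 points). The rule uses the adjusted result if triggered and chi-squared otherwise.

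| Setting | Covariates | Rule | Always adjusted | Gain |
|---|---|---|---|---|
| Errors 64% v 32% | weak | 94.2% | 94.9% | 0.7 |
| | strong | 94.7% | 96.9% | 2.2 |
| ADEs 87% v 58.3% | weak | 95.0% | 95.1% | 0.1 |
| | strong | 95.6% | 97.0% | 1.4 |
| Errors 64% v 40% (assumed) | weak | 74.9% | 76.3% | 1.4 |
| | strong | 75.8% | 81.3% | 5.5 |

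A separate run gave gains of 0.7/2.2, 0.5/1.5 and 1.8/5.7 points (weak/strong). At 52 per arm, with ten baseline variables tested and two of them prognostic (odds ratio 1.5, 2 or 3 per SD), the gains for errors at the planned effect were 93.5 − 92.6 = 0.9, 95.8 − 93.4 = 2.4 and 97.5 − 94.8 = 2.7 points.

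**4. How often the choice of result matters.** With two candidates, once the trigger has fired, the two tests disagree on p<0.05 in 4–8% of trials for errors, 4–7% for ADEs and 14–21% at 64% v 40%. Over all trials that is at most 0.0975 × 0.08 = 0.8% for errors at the planned effect, and 0.0975 × 0.21 = 2.0% at the smaller one.

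**5. Type I error.** With two to four candidates at 58 per arm, the rule gives 4.5–5.2%, and taking the more favourable result after a trigger gives 4.9–5.5%. With ten candidates at 52 per arm (5,000 trials, error about 0.3 points), the rule gives 5.1–5.7% and the more favourable result 6.4–6.9%. In those same runs the plain chi-squared test rejected in 5.3–5.7%, so only part of the excess comes from the choice.

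**6. How many covariates the data can carry.** ADE non-events: 58 × (0.13 + 0.417) = 31.7. Arm plus two covariates gives 31.7/3 = 10.6 per parameter; arm plus four gives 31.7/5 = 6.3. Acute rejection at F1's 12% v 9%: 58 × 0.21 = 12.2 events, or 12.2/3 = 4.1 per parameter, which is too few.

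**7. Estimated GFR.** Adjusting for baseline multiplies the confidence interval width by √(1 − r²): 0.866 at r = 0.5 and 0.714 at r = 0.7 (correlations assumed), that is 13% or 29% narrower.

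**8. Behaviour of the proposed analysis under no effect (two covariates).** The logistic arm term rejects in 5.0% of trials at 64% in both arms and 4.1–4.4% at 87%. The standardised risk difference rejects in 5.9–6.4% with a plain z interval, and in 5.2–5.7% with an n/(n−p) variance and t quantile.

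**The case against.** The case for leaving the text alone is that little turns on it. Power is ample, the gains at the planned effects are small, and the larger ones need an effect that the plan does not assume or covariate strengths that it does not give. F3 can also fairly be read as letting the adjusted model supersede the unadjusted test, and that reading holds type I error close to 5%. This stands as an argument about size. It does not settle which result is primary, because F4 restates the unadjusted comparison without any condition.

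Three stronger readings are tempting, and the documents do not support them.

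- A reader might infer that F3 proposes a baseline-response model for errors and ADEs, which have no baseline assessment in E2, or that it concedes lost precision on them. Both statements sit within the linear-regression text and concern continuous outcomes only.
- A reader might infer from the absence of a survey row in E2 that the surveys have no baseline measurement. E2 has a general row for baseline patient information, and the forms may be in the attachments, so nothing follows.
- A reader might infer that adjustment should become primary for every outcome. The 4.1 rejection events per parameter argue against that.

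Any new primary model must also work with F3's multiple imputation and its inclusion of all randomised patients. The fix covers this.

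**Conclusion.** The point holds as a modest but real weakness, worth correcting because correction costs almost nothing. The trigger is undefined, imbalance is a poor criterion, and the primary result is undetermined for both powered binary outcomes if the trigger fires.

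At 58 per arm with two covariates of assumed strength, the power forgone is about 0 to 2 points at the planned effects and 1.4 to 5.7 points at an assumed 64% v 40%. It should not be presented as a threat to the stated power. Nor is it a type I error problem under the literal rule: inflation appears only if the more favourable result may be picked, and its size (about 5 to 5.5% with two to four candidates, 6.4–6.9% with ten) depends on a number of variables that the documents do not give. For exploratory estimated GFR the gain in precision is larger, subject to the assumed correlation.

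**What to change.** Delete both conditional sentences and the open-ended risk-factor list from F3, and put this text in F3 and F4:

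> Baseline tables are descriptive and do not trigger adjustment. For the incidence of medication errors and of grade 3+ ADEs, the primary analysis is a logistic model with arm and at most two baseline covariates, chosen on prognostic grounds from information collected before randomisation and fixed before the first by-arm report. The p-value is that of the arm term. The effect is the covariate-standardised risk difference with a 95% CI using an n/(n−p) variance correction and t quantile, computed within each imputed data set and combined across imputations. The unadjusted chi-squared or Fisher test is a sensitivity analysis. Healthcare encounters use the planned Poisson or negative binomial model with the same covariates. Estimated GFR is always adjusted for its baseline value. Rare outcomes (acute rejection, graft loss, death) keep the planned unadjusted comparison.

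Severity comparisons and other ADE grades stay as planned. The investigators choose the covariates.

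The cost is wording only, with no added patients or visits. If one of the E4 survey variables is chosen, it must be measured before randomisation and its timing written into the E2 schedule. Because the p-value and the interval come from different calculations, they can disagree at the margin; the text above makes the arm-term p-value the test.

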Oxycodone 5 mg	1	5	mg	Tablet	Oral	4	As Needed	For Severe Pain		 Edit	 Delete
Pepcid 20 mg	30	20	mg	Tablet	Oral	2	Scheduled	Prevent Upset Stomach		 Edit	 Delete
Prednisone 10 mg	30	10	mg	Tablet	Oral	1	Scheduled	Prevent Rejection		 Edit	 Delete
Prograf 5 mg	1	5	mg	Capsule	Oral	2	Scheduled	Prevent Rejection	Take after labs No Grapefruit	 Edit	 Delete
Prograf 1 mg	60	1	mg	Capsule	Oral	2	Scheduled	Prevent Rejection	Take after labs No Grapefruit	 Edit	 Delete
Valacyte 450 mg	30	450	mg	Tablet	Oral	1	Scheduled	Prevent Infection		 Edit	 Delete

1 - 9 of 9 items

11:47 AM
9/15/2016

[figure not shown]
Page to manage medication scheduling for a specific patient

Medications

Name	Quantity	Strength	Unit	Form	Route	Frequency	Schedule	Indication	Instructions	Actions
Bactrim 400/80 mg	30	400/80	mg	Tablet	Oral	1	Scheduled	Prevent infection	 Edit  Delete	
Celicept 250 mg	120	250	mg	Capsule	Oral	2	Scheduled	Prevent Rejection	May cause diarrhea  Edit  Delete	
Nystatin 100,000 units/ml	600	100,000	units/ml	Suspension	Oral	4	Scheduled		 Edit  Delete	
Oxycodone 5 mg	1	5	mg	Tablet	Oral	4	As Needed	For Severe Pain	 Edit  Delete	
Pepcid 20 mg	30	20	mg	Tablet	Oral	2	Scheduled	Prevent Upset Stomach	 Edit  Delete	
Prednisone 10 mg	30	10	mg	Tablet	Oral	1	Scheduled	Prevent Rejection	 Edit  Delete	
Prograf 5 mg	1	5	mg	Capsule	Oral	2	Scheduled	Prevent Rejection	Take after labs No Grapefruit  Edit  Delete	
Prograf 1 mg	60	1	mg	Capsule	Oral	2	Scheduled	Prevent Rejection	Take after labs No Grapefruit  Edit  Delete	
Valacyte 450 mg	30	450	mg	Tablet	Oral	1	Scheduled	Prevent infection	 Edit  Delete	

